#### **7.1.2. Adverse Event Severity**

Adverse events are graded by the investigator as Grade 1, 2, 3, 4, or 5 according to Common Terminology Criteria for Adverse Events (CTCAE) Version 5.0. The severity grade of events for which the investigator did not record severity will be categorized as “missing” for tabular summaries and data listings. The missing category will be listed last in summary presentation.

#### **7.1.3. Relationship of Adverse Events to Study Drug**

Related AEs are those for which the investigator selected “Related” on the AE CRF to the question of “Relationship to Study Drug(s).” Relatedness will always default to the investigator’s choice, not that of the medical monitor. Events for which the investigator did not record relationship to study drug will be considered related to study drug for summary purposes. However, by-participant data listings will show the relationship as missing.

#### **7.1.4. Serious Adverse Events**

Serious adverse events (SAEs) will be identified and captured as SAEs if the AEs met the definitions of SAEs that were specified in the study protocol. SAEs captured and stored in the clinical database will be reconciled with the safety database before data finalization.

#### **7.1.5. Treatment-Emergent Adverse Events**

##### **7.1.5.1. Definition of Treatment-Emergent Adverse Events**

Maternal treatment-emergent adverse events (TEAEs) are defined as AEs that start or deteriorate on or after the first dose of study medication and no later than 7 days following the last dose of study medication. For any participants (i.e., mothers) who die during the study and the date of death is between the date of the first dose of study medication and the date of study discontinuation (as entered by the site), inclusive, all AEs (including those

resulting in death) that occur during the study will be considered as TEAEs irrespective of the last dose and will be included in the TEAE summaries. All summaries of AEs will be based on TEAEs unless specified otherwise.

For newborns, all reported AEs will be considered TEAEs for the purpose of summaries.

#### 7.1.5.2. Incomplete Dates

If the onset date of the AE is incomplete and the AE stop date is not prior to the first dose of study drug, then the month and year (or year alone if month is not recorded) of onset determine whether an AE is treatment emergent. The event is considered treatment emergent if both of the following 2 criteria are met:

- The AE onset is the same as or after the month and year (or year) of the first dosing date of study drug, and
- The AE onset date is the same as or before the month and year (or year) of the date corresponding to 7 days after the date of the last dose of study drug

An AE with completely missing onset and stop dates, or with the onset date missing and a stop date later than the first dosing date of study drug, will be considered to be treatment emergent. In addition, an AE with the onset date missing and incomplete stop date with the same or later month and year (or year alone if month is not recorded) as the first dosing date of study drug will be considered treatment emergent.

#### 7.1.6. Summaries of Adverse Events and Deaths

Treatment-emergent AEs will be summarized based on the Safety Analysis Set.

##### 7.1.6.1. Summaries of AE Incidence

The number and percentage of participants who experienced AEs described below will be provided and summarized by SOC and PT unless otherwise indicated:

- TEAEs
- TEAEs of Grade 3 or higher (by SOC, PT and maximum severity)
- Treatment-related TEAEs (TRAEs)
- TRAEs of Grade 3 or higher (by SOC, PT and maximum severity)
- Serious TEAEs
- Serious TRAEs
- TEAEs leading to discontinuation of study drug

- TEAEs leading to death
- AESIs
- ECIs

A brief, high-level summary of AEs described above will be provided by the number and percentage of participants who experienced the above AEs.

Multiple events will be counted only once per participant in each summary. Adverse events will be summarized and listed first in alphabetic order of SOC and then by PT in descending order of total frequency within each SOC. For summaries by severity, the most severe severity will be used for those AEs that occurred more than once in a given participant during the study.

In addition to the above summary tables, TEAEs, TEAEs of Grade 3 or higher, TRAEs, TRAEs of Grade 3 or higher, serious TEAEs, TEAEs leading to discontinuation of study drug, AESIs, and ECIs will be summarized by PT only in descending order of total frequency within indication.

Furthermore, data listings will be provided for the following:

- All AEs, indicating whether the event is treatment emergent
- All AEs of Grade 3 or higher
- TRAEs
- TRAEs of Grade 3 or higher
- AESIs
- ECIs
- SAEs
- AEs leading to death (ie, outcome of death)
- AEs leading to discontinuation of study drug

If there are no participants who meet the criteria for any of these listings, the listing will be generated and will contain a statement, “No <criteria> were reported.” For example, if there are no AEs leading to death on study, the statement would be “No AEs leading to death were reported.”

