##### **10.4.2.1. Adverse Events**

In general, TEAEs are defined as AEs that start or deteriorate on or after the first dose of study medication and no later than 7 days following the last dose of study medication. For any participants (i.e., expectant mothers) who die during the study and the date of death is between the date of the first dose of study medication and the date of study discontinuation (as entered by the site), inclusive, all AEs (including those resulting in death) that occur during the study will be considered as TEAEs irrespective of the last dose and will be included in the TEAE summaries. All summaries of AEs will be based on TEAEs unless specified otherwise.

The complete list of Preferred Terms for AESIs and ECIs (as described in [Sections 9.2.6](#) and [9.2.7](#)) will be outlined in the SAP and summarized.

AEs will be coded using MedDRA. The number and proportion of participants who experience the event according to MedDRA System Organ Class (SOC) and Preferred Term will be presented by treatment group.

The incidence of all AEs and treatment-related AEs will be tabulated by treatment received. These AEs will be classified by SOC and Preferred Term using MedDRA. AEs will be graded using the CTCAE, Version 5.0, grading scale. For incidence reporting, if a participant reported >1 AE that was coded to the same SOC or Preferred Term, the participant will be counted only once for that specific SOC or Preferred Term. An overview of AEs and TEAEs, both of which include participant incidence of AEs, treatment-related AEs, AEs by severity, AESIs, ECIs, SAEs, deaths, and AEs that lead to discontinuation, will be presented.

Furthermore, exposure-adjusted incidence rates (EAIR) will be provided for each AE reported. For EAIR analyses, the following convention will be used to calculate the denominator (i.e., population-level time at-risk) for these analyses. The population-level time at-risk includes only the time each participant is at risk. The start date of at-risk time is the date of first dose of study drug, and the last date of at-risk time is the start date of the occurrence of the AE or is censored at completion/early termination, whichever is earlier.

While no formal hypothesis testing or margin selection is planned, the risk difference and corresponding exact 95% CI (using the method of Chan and Zhang [1999]) will be presented to compare treatment groups with regards to AESIs and ECIs.

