#### **10.4.2.3. Laboratory Assessments**

Clinical safety laboratory values will be measured by a central laboratory and, where grading criteria apply, will be graded according to the CTCAE grading scale. Summary statistics for actual values and for changes from baseline will be tabulated for laboratory results by scheduled visit. Graphs of laboratory values over time may also be produced.

Participants with clinical laboratory values outside of the normal reference range at any postbaseline assessment will be summarized, including by the CTCAE and, if necessary, other grading scales. Shifts from baseline laboratory values will be tabulated. The observed vital sign data, the change from baseline, and those meeting criteria for potentially clinically significantly abnormal criteria for each measurement will be summarized with descriptive statistics.

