### **1.1.3. Safety Objective and Endpoints**

- To assess the safety and tolerability of VLX in participants with ICP on the basis of the following endpoints:
  - Incidence of treatment-emergent adverse events (TEAEs), serious adverse events (SAEs), adverse events of special interest (AESIs), events of clinical interest (ECIs), and AEs that lead to discontinuation of study drug
  - Incidence of clinically significant laboratory abnormalities

Note: Safety and tolerability are primary objectives for the open-label supplemental cohort.

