### **7.2. Laboratory Evaluations**

Laboratory data collected during the study will be analyzed and summarized using both quantitative and qualitative methods. Summaries of laboratory data will be provided for the Safety Analysis Set and will include data collected up to the last dose of study drug plus 7 days for participants who have permanently discontinued study drug, or all available data at the time of the database snapshot for participants who were ongoing at the time of an interim analysis. The analysis will be based on values reported in conventional units. When values are below the LOQ, they will be listed as such, and the closest imputed value will be used for the purpose of calculating summary statistics as specified in [Section 3.7](#). Hemolyzed test results will not be included in the analysis, but they will be listed in by-participant laboratory listings.

A by-participant listing for laboratory test results will be provided by participant ID number and time point in chronological order for hematology, serum chemistry, and urinalysis separately.

No formal statistical testing is planned.

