## **7.6. Changes From Protocol-Specified Safety Analyses**

There are no deviations from the protocol-specified safety analyses.

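### SAP 7.1.6.1 omits the by-arm overview of all maternal AEs and SAEs that the protocol requires, and SAP 7.2 stops laboratory summaries 7 days after last dose for women who discontinued drug

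*SAP*

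**What the plan says.** **Adverse events.** Protocol 10.4.2.1 defines TEAEs as ending 7 days after the last dose and makes them the default for AE summaries. It then goes beyond that default. It has all AEs, as well as treatment-related AEs, tabulated by treatment received, and it calls for "An overview of AEs and TEAEs, both of which include participant incidence of AEs, treatment-related AEs, AEs by severity, AESIs, ECIs, SAEs, deaths", together with AEs leading to discontinuation.

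SAP 7.1.5.1 repeats the 7-day maternal window and the default: "All summaries of AEs will be based on TEAEs unless specified otherwise". SAP 7.1.6.1 then tabulates TEAEs, treatment-related TEAEs, serious TEAEs, serious treatment-related TEAEs, TEAEs leading to discontinuation or death, AESIs and ECIs. Its overview is drawn from that list: "A brief, high-level summary of AEs described above will be provided by the number and percentage of participants who experienced the above AEs". All AEs and all SAEs appear only among the listings. SAP 1.1.3 nevertheless names SAE incidence as a safety endpoint separate from TEAE incidence.

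**Laboratory data.** Protocol 10.4.2.3: "Participants with clinical laboratory values outside of the normal reference range at any postbaseline assessment will be summarized". SAP 7.2 says its laboratory summaries "will include data collected up to the last dose of study drug plus 7 days for participants who have permanently discontinued study drug". The only stated alternative is for women still ongoing at an interim analysis. The shift tables in SAP 7.2.2 fall under this rule.

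**Declaration.** SAP 7.6: "There are no deviations from the protocol-specified safety analyses". SAP 1 states that the plan was written against protocol Version 1 of 14 October 2020.

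**The concern.** The trial collects maternal safety data well past the point where the SAP stops tabulating them. Protocol 8.3.1 runs AE collection to the later of F2 and up to 30 days after hospital discharge. The Schedule of Activities keeps women who stop drug early on weekly visits through delivery, F1 and F2. It also schedules hematology, chemistry, coagulation and vitamins A, D and E at F2.

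A maternal SAE that starts on the eighth day after last dose or later would therefore be collected but never counted by arm as an SAE. Liver and vitamin results from more than 7 days after a permanent stop would leave the shift tables. These are the results a safety reader wants most: protocol 9.2.7 makes Grade 3 or higher transaminase increases and fat-soluble vitamin deficiency events of clinical interest, and protocol Appendix 3 requires repeated liver tests after drug is stopped for suspected liver injury.

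**Working it through.** The plan gives no figure on this point, so there is nothing to reproduce. The check is a comparison of texts, followed by day arithmetic to show the scale.

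**1. Which by-arm table holds a late maternal SAE?**
- The serious-event rows in SAP 7.1.6.1 are serious TEAEs and serious treatment-related TEAEs. Both need onset no later than last dose + 7 days. Exceptions are women who die on study, and some incomplete dates under SAP 7.1.5.2.
- The AESI and ECI rows do not carry the word treatment-emergent. They are restricted only through the default in SAP 7.1.5.1.
- The exposure-adjusted rates in SAP 7.1.7 cover each reported AE and may pick up late events by term. They are not an SAE table or an overview.
- So no by-arm SAE table contains the event, although protocol 10.4.2.1 asks for an all-AE overview with SAEs in it.

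**2. Whose laboratory results are cut?**
- Early stoppers: the SAP 7.2 wording applies to them directly.
- Women dosed to delivery: every woman has stopped drug by the final analysis. If the first limb of the SAP 7.2 sentence does not cover these women, no limb does. The more natural reading is that it does. F2 is at 28 ± 3 days, so the earliest F2 is 28 − 3 = day 25 after delivery, later than day 7.

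**3. Calendar share, women dosed to delivery** (last dose on the day of delivery, T days on drug, F2 on day 28 after delivery). Days outside the window = 28 − 7 = 21; share = 21/(T + 28).

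| Case | Outside / collected | Share |
|---|---|---|
| T = 21 | 21/49 | 43% |
| T = 21, F2 on day 25 | 18/46 | 39% |
| T = 21, F2 on day 31 | 24/52 | 46% |
| T = 21, collection to 30 days after same-day discharge | 23/51 | 45% |
| T = 28 | 21/56 | 38% |
| T = 42 | 21/70 | 30% |

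All of these outside days are postpartum.

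**4. Draws, woman dosed to delivery on day 21** (on the more natural reading of SAP 7.2). Chemistry: Week 1, Week 2, Week 3/delivery, F2, so 1 of 4 is excluded. Vitamins: delivery and F2, so 1 of 2 is excluded.

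**5. Illustrative early stopper** (assumed: last dose day 7, delivery day 28 taken as the Week 4 visit, F2 day 56). Cut-off = 7 + 7 = day 14.
- Chemistry on days 7, 14, 21, 28 and 56: 3 of 5 are excluded, 2 of them before or at delivery. If a separate early-termination draw is taken inside the window, this becomes 3 of 6.
- Vitamins on days 28 and 56: both are excluded, so she contributes no post-baseline vitamin value.
- AE window: 14 of 56 days are inside and 56 − 14 = 42 outside, of which days 15 to 28 (14 days) are still in pregnancy.

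**6. Would lifting the cut-off be enough?** SAP 3.8.2 exempts only the delivery visit from its windows, and Tables 2 and 5 have no F2 row. Delivery on protocol day 21 is SAP Day 22, so F2 is SAP Day 22 + 28 = 50. Table 2 Week 7 runs from 7×7 − 2 = 47 to 7×7 + 4 = 53. Table 5 Week 8 runs from 6×7 + 2 = 44 to 10×7 + 1 = 71. A postpartum F2 value would be pooled with pregnancy values at Week 7 (chemistry) or Week 8 (vitamins). F2 therefore needs its own visit.

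**The case against.** The strongest replies, and what stands of each:

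- **The laboratory cut may not reach women dosed to delivery.** SAP 4.1 separates completing study drug from premature discontinuation, protocol 7.1 does not list delivery as a reason for discontinuation, and SAP 7.2.1 promises values at each post-baseline time point. This stands as a genuine ambiguity. A reader might infer that the SAP flatly excludes every F2 result; the text does not settle that. Only the cut for early stoppers is clear.
- **AESIs and ECIs are better covered than SAEs.** Their rows lack the TEAE label, and SAP 7.1.7 gives by-arm risk differences with exact intervals for both. A reader might infer that late AESIs and ECIs get no by-arm comparison. That follows only if the general default is applied to them, so the SAE gap is the firm one.
- **Vitamins and coagulation are not lost.** The SAP 7.2 listing is described as "in chronological order for hematology, serum chemistry, and urinalysis separately" and names neither, but protocol 10.4.2 requires all safety data to be listed. A reader might infer that these values have no output at all; the protocol says otherwise. This is a wording point only.
- **The SAP 7.6 statement may have been true when written.** Version 1 of the protocol is not among the documents. The statement can be called incorrect against the supplied protocol, and no further.
- **Days are not risk.** The uncounted time is off drug and, for women dosed to delivery, postpartum. Volixibat is minimally absorbed, and the 7-day window is the protocol's own. All of this stands: 43% of days does not mean 43% of events.

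None of this supplies the missing all-AE and SAE overview or reconciles the laboratory cut with protocol 10.4.2.3.

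**Conclusion.** The point holds against the supplied protocol. Followed as written, SAP 7.1.6.1 leaves maternal SAEs starting more than 7 days after last dose out of every by-arm SAE table. SAP 7.2 leaves post-discontinuation liver and vitamin results of early stoppers out of the shift tables, and probably the F2 results of women dosed to delivery as well.

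The size in women or events is unknown, because the documents give neither an early-stopping rate nor a late-event rate. The day and draw counts above illustrate schedules under assumed dates and are not estimates of missed events. Onset in the first 7 days after last dose still counts. All AEs in mothers who die on study count, and so do all newborn AEs. Efficacy and the perinatal composite are untouched. The likely cause is a SAP not updated from protocol Version 1. It should be corrected before Part 2 is unblinded, and confidence is highest for the SAE overview and the early stoppers.

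**What to change.** Keep the TEAE tables as they are, and:

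1. In SAP 7.1.6.1, add a by-arm overview of all maternal AEs, SAEs, AESIs and ECIs from first dose to the end of AE collection.
2. In SAP 7.2, include all postbaseline values in the out-of-range and shift summaries, with no cut at last dose plus 7 days. Make F2 its own visit with its own shift table, outside the pregnancy windows of SAP 3.8.2.
3. Update the SAP to the current protocol version and correct SAP 7.6 accordingly.

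Minor wording, which does not carry the point: name vitamins and coagulation in the SAP 7.2 listing. In SAP 7.1.7, state that censoring is at study completion or study termination, and count events for the exposure-adjusted rate over the same period.

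The cost is SAP text, one AE overview table, an F2 row and an extra shift table. No new data are needed.

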### **7.1.7. Additional Analysis of Adverse Events**

Furthermore, exposure adjusted incidence rates (EAIR) will be provided for each AE reported. For EAIR analyses, the following convention will be used to calculate the denominator (i.e., population-level time at-risk) for these analyses. The population-level time at-risk includes only the time each participant is at risk. The start date of at-risk time is the date of first dose of study drug, and the last date of at-risk time is the start date of the occurrence of the AE or is censored at completion/early termination, whichever is earlier.

While no formal hypothesis testing or margin selection is planned, the risk difference and corresponding exact 95% CI (using the method of Chan and Zhang [1999]) will be presented to compare treatment groups with regards to AESIs and ECIs.

The TEAE by PT summary will also be repeated by the subgroups defined in [Section 3.4](#).

Incidence/prevalence plots of common adverse events may be explored.

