### 1.3. Schedule of Activities

**Table 1 Schedule of Activities**

Visit Name	Screening	Treatment Period				Follow-Up		Notes
		Baseline	Weeks 1, 2, 3, etc.	Early Termination*	EOT/Delivery	F1	F2 (EOS)	
Day/Week (Window)	Day -10 to -1	0*	Every 7 Days (±1 Day) Until Delivery		Day of Delivery (+2 Days)	Phone Call: 14 Days after Delivery (±3 Days)	Clinic Visit: 28 Days after Delivery (±3 Days)	
*Participants who early terminate from study drug should still continue with weekly visits through delivery, F1, and F2.
 
Some visits may be conducted as a home health or remote visit at the discretion of the investigator upon approval by the sponsor or designee and in accordance with local and regional regulations.
 
*See Section 8.1.8 for further details on timing of baseline visit.

Administrative Procedures								
Informed consent	X							
Eligibility Procedures								
Inclusion/exclusion criteria	X	X						
Demography	X							
Prior/concomitant treatment	X	X	X	X	X	X	X	
Medical history	X	X						Includes menstrual and obstetric history
Estimated gestational age assessment	X							Confirmation of eligibility based upon estimated gestational age required before randomization: CRL from early ultrasound or head circumference on ultrasound if CRL is >84 mm.

Visit Name	Screening	Treatment Period				Follow-Up		Notes
		Baseline	Weeks 1, 2, 3, etc.	Early Termination*	EOT/Delivery	F1	F2 (EOS)	
Day/Week (Window)	Day -10 to -1	0*	Every 7 Days (±1 Day) Until Delivery		Day of Delivery (+2 Days)	Phone Call: 14 Days after Delivery (±3 Days)	Clinic Visit: 28 Days after Delivery (±3 Days)	*Participants who early terminate from study drug should still continue with weekly visits through delivery, F1, and F2.  Some visits may be conducted as a home health or remote visit at the discretion of the investigator upon approval by the sponsor or designee and in accordance with local and regional regulations. *See Section 8.1.8 for further details on timing of baseline visit.
Hepatitis and HIV screen, TSH	X							If HIV results are documented as negative from the current pregnancy in a participant deemed to be low risk by the investigator, HIV at screening visit may be waived.
Dosing Procedures								
Randomization		X						
Study drug dispensing		X	X					As needed
Study drug collection/reconciliation			X	X	X			As needed
Efficacy Procedures								

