## **4.2. End of Study Definition**

The end of the study is defined as the date of the last visit of the last participant in the study. The end of study for individual participants is the completion of the follow-up period after the day of delivery, including completion of follow-up Visit 2 (F2).

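### The person-time rule for maternal exposure-adjusted AE rates is not matched to the treatment-emergent window that limits which events are counted by default

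*SAP*

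**What the plan says.** **Events.** SAP 7.1.5.1 counts a maternal AE as treatment-emergent if it starts or worsens on or after the first dose and "no later than 7 days following the last dose of study medication" (with an exception for maternal deaths). It then sets a default: "All summaries of AEs will be based on TEAEs unless specified otherwise". Protocol 10.4.2.1 has the same window and default. For newborns, SAP 7.1.5.1 treats every reported AE as treatment-emergent, with no 7-day limit.

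**Rates.** SAP 7.1.7 says that "exposure adjusted incidence rates (EAIR) will be provided for each AE reported". Time at risk starts at the first dose. For its end, SAP 7.1.7 says that "the last date of at-risk time is the start date of the occurrence of the AE or is censored at completion/early termination". In protocol 10.4.2.1 it likewise ends at AE onset or "is censored at completion/early termination, whichever is earlier". SAP 7.1.7 also states a principle: "The population-level time at-risk includes only the time each participant is at risk".

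**Follow-up.** Treatment ends on the day of delivery (protocol 4.1). A participant's study ends with "completion of the follow-up period after the day of delivery", including visit F2 (protocol 4.2), which the schedule of activities places 28 ± 3 days after delivery. Stopping drug early does not end follow-up: "Participants who early terminate from study drug should still continue with weekly visits through delivery, F1, and F2".

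**The concern.** A rate per unit of exposure needs events and time drawn from the same period. Here the event window closes 7 days after the last dose, while the clock is stopped by a different, undefined event. If the clock runs to F2, a participant treated to delivery contributes about three further weeks in which no maternal event can enter the numerator. That contradicts the plan's own principle that only time at risk is counted. SAP 7.2 does cut laboratory summaries at last dose + 7 days, so the missing cut in 7.1.7 is an internal inconsistency.

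The purpose of an EAIR is to make arms with different exposure comparable. A mismatch that itself depends on time on drug defeats that purpose. Durations could plausibly differ: protocol 6.8.1.1 is concerned with early stopping for gastrointestinal symptoms, and protocol 8.1.12 ties planned delivery partly to bile acid levels, which volixibat is meant to lower.

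**Working it through.** Neither document states an EAIR figure, so there is none to reproduce.

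**Inputs from the documents**
- Maternal event window: first dose to last dose + 7 days (SAP 7.1.5.1).
- Drug ends at delivery (protocol 4.1); F2 is at delivery + 28 ± 3 days (protocol Table 1).
- Relatively few participants are expected to stay on treatment beyond 3 weeks (protocol 4.3.2.1), so L = 21 days on drug is the central case.

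**Assumptions (the documents give no values).** Constant hazard within the event window, treatment to delivery unless stated, and the stopping shares and AE risks shown below.

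**Matched rate.** Events and time both end at last dose + 7, giving L + 7 countable days.

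**Study reading (time to F2).** For a rare event, planned rate ÷ matched rate = (L+7)/(L+28). **Study-drug reading (time to last dose).** The ratio is at most (L+7)/L. It is an upper limit because the plan does not say whether an event starting after the censoring date would still be counted.

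| Days on drug, L | Study reading | Study-drug reading (maximum) |
|---|---|---|
| 14 | 21/42 = 0.50 | 21/14 = 1.50 |
| 21 | 28/49 = 0.57 | 28/21 = 1.33 |
| 28 | 35/56 = 0.63 | 35/28 = 1.25 |
| 42 | 49/70 = 0.70 | 49/42 = 1.17 |

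At L = 21, the F2 window of ± 3 days moves 0.57 between 28/52 = 0.54 and 28/46 = 0.61.

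**Commoner events (study reading, L = 21).** Time stops at the first event, so the dilution is smaller. With AE risks of 5%, 20% and 50% per 28 days, the ratio is 0.58, 0.60 and 0.66. In absolute terms, at 10% per 28 days:
- hazard = −ln(0.9)/28 = 0.00376 per day, so the matched rate is 3.76 per 1000 person-days;
- time to F2 adds 0.9 × 21 = 18.9 days to the 0.1/0.00376 = 26.6 days inside the window, so the planned rate is 0.1/45.5 = 2.20 per 1000 person-days.

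**Between arms with equal true hazards (study reading)**
- Same durations, no early stopping: rate ratio 1.00.
- One arm treated 28 days, the other 21: 0.625/0.571 = 1.09 for a rare event, 1.10 at 10% risk per 28 days.
- Everyone delivers on day 21, but 20% of one arm stop drug on day 7. Each of these has 14 countable days out of 49. The arm averages 0.2 × 14 + 0.8 × 28 = 25.2 countable days, so the ratio is (25.2/49)/(28/49) = 0.90. With 10% or 30% stopping it is 0.95 or 0.85.

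With time capped at last dose + 7, each of these ratios is 1.00.

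**All-AE reading.** If every reported maternal AE counts and time runs to study completion, the 7-day mismatch largely disappears. A small one can remain, because AE collection runs to the later of F2 and 30 days after hospital discharge (protocol 8.3.1), which can fall after F2.

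**The case against.** The strongest reply is that SAP 7.1.7 may not use TEAEs at all. It refers to each AE reported, the TEAE default yields where something else is specified, and protocol 10.4.2.1 separately mentions an overview of AEs and of TEAEs. With all AEs counted to study completion, numerator and denominator would broadly agree. This reading is possible, but the wording does not clearly override the default, and neither document says that it does.

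The end of the clock is also open. SAP 4.1 lists completion of study drug and of the study phase separately. The schedule uses early termination for study drug, whereas protocol 7.2 applies the early termination visit to study withdrawal. This settles the direction of the error only if one reading is chosen; with TEAEs counted, neither reading gives a match.

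Two stronger inferences should not be drawn:
- A reader might infer that every EAIR is too low. The documents do not support that. The study-drug reading can make rates too high, the all-AE reading leaves little mismatch, and newborn AEs have no 7-day limit.
- A reader might infer that the arms will be compared unfairly, for instance from a spurious ratio of 0.625/0.50 = 1.25 for 28 against 14 days on drug. No passage supports a two-fold difference in duration, and with equal hazards and equal durations the ratio is 1.00.

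It is also true that little rests on EAIRs. The main AE tables are counts and percentages (SAP 7.1.6.1). The between-arm comparison specified for AESIs and ECIs is a risk difference with an exact interval, which does not use person-time. No test or success criterion depends on an EAIR.

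**Conclusion.** The point holds for maternal AEs. Under the plan's default numerator, the stated censoring rule gives mismatched rates on either consistent reading of its end point: about 0.57 of the matched rate at 21 days on drug if it means the study, and up to 1.33 times if it means study drug. For the same 21-day participant without an event, time at risk is 49 or 21 days. This is more than a missing detail, because the rule as written does not correct for unequal exposure.

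The sizes assume a rare event, constant hazard and treatment to delivery. Distortion between arms with equal hazards requires different drug durations; 1.10 and 0.90 illustrate it and do not predict it. The consequence is limited to descriptive safety tables. It should be corrected before unblinding and does not affect the efficacy conclusions.

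**What to change.** In protocol 10.4.2.1 and SAP 7.1.7:
- State that maternal EAIRs count TEAEs.
- End maternal time at risk at the earliest of first onset of that AE, last dose + 7 days, and study exit.
- Give newborn AEs their own rule: time from birth to first onset or the end of newborn AE follow-up. Applying the maternal cut-off to newborns would create a new mismatch.
- If all maternal AEs are intended instead, say so and end time at risk at the end of AE collection.

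The cost is a short definition in each document and a change to the derivation of time at risk. The first-dose, last-dose and AE onset dates are already needed to classify TEAEs, so maternal rates need no new data. Only descriptive tables change.
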